9.3. Populations for Analyses

This table describes the populations that will be used for statistical analyses within each ISA of the master protocol. Additional intervention-specific populations for analyses may be described in the ISAs.

Population	Description
Entered	All participants who sign the ICF for an ISA
Enrolled (ITT)	All participants randomly assigned to an ISA
Modified ITT (mITT)	All enrolled participants who take at least 1 dose of study intervention within an ISA. Participants will be analyzed according to the intervention they are randomly assigned.
Safety	All enrolled participants who take at least 1 dose of study intervention within an ISA. Participants will be analyzed according to the intervention they receive.
Enhanced ITT	This population includes all participants from the modified ITT population and participants from the supplementary ISAs that are used to borrow placebo/treatment effect information for the ISA of interest
Biomarker Evaluable	All participants within the subset of participants from the biomarker of interest from whom a valid assay result has been obtained within an ISA
Per-Protocol	Some ISAs may define this population, and details will be provided in the ISA or ISA SAP. Generally, participants will be required to have a certain level of compliance with the master protocol and ISA to be included in the population

Abbreviations: ICF = informed consent form; ISA = intervention-specific appendix; ITT = intention to treat; SAP = statistical analysis plan.

9.4. Statistical Analyses

9.4.1. General Considerations

Statistical analysis of the master protocol and ISAs will be the responsibility of the sponsor or its designee.

Multiple statistical analysis plans (SAPs) will be defined and used throughout the duration of the entire master protocol. A single master protocol SAP will be developed, as well as an ISA SAP, for each ISA.

The master protocol SAP describes the statistical analyses that are common across the entire master protocol, and the analyses will be conducted within each ISA. The analyses in the master protocol SAP will include

- disposition reports
- AE analyses
- laboratory analyses
- vital signs analyses, and
- efficacy analyses that do not specify borrowing of placebo or treatment-effect information from other ISAs.

A DSA SAP will not be developed. The DSA-specific analyses will be provided in the ISA SAP.

The ISA SAP will contain the statistical analyses unique for each ISA and will include

- the proposed strategy of borrowing placebo and/or treatment-effect information from other ISAs
- if borrowing of placebo or treatment effect information is implemented, the Bayesian model and exact prior distributions used for the primary efficacy analysis and other Bayesian secondary analyses, and
- details of analyses that are unique to the ISA or analyses that may differ from what is specified in the master protocol SAP.

If there is a discrepancy between the master protocol SAP and the ISA SAP, the methodology in the ISA SAP will be used.

Changes to the master protocol data analysis methods will require an amendment only if they change a principal feature of the master protocol. Any other change to the data analysis methods, and the justification for making the change, will be described in the respective SAP and the clinical study report for each respective ISA. Additional exploratory analyses of the data will be conducted as deemed appropriate.

The master protocol SAP will be finalized prior to the unblinding of the first ISA. Any updates to the master protocol SAP will be finalized prior to the unblinding of the respective ISA.

The ISA SAP will be finalized prior to the first unblinding of the respective ISA.

The specific baseline definitions for each analysis will be provided in the master protocol SAP.

No adjustments for multiplicity will be performed unless specified in the ISA SAP.

If the primary efficacy analysis dataset for an ISA includes data from repeat participants, all available data for the repeat participants will be included and used in the model. A participant by ISA-specific random effect (or other appropriate adjustments) will be added to the primary efficacy analysis model to account for the repeat participants. Specific details will be provided in each ISA SAP.

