4.2. Scientific Rationale for Study Design

The master protocol construct will

- offer flexibility to continually add different interventions at different time points across different participant populations
- enable efficient testing of multiple promising targets across multiple pain states
- allow direct statistical comparisons of interventions studied within a pain type
- enable borrowing of
 - placebo participants within a pain type, and
 - treatment-effect information across pain types for a given intervention
- facilitate smaller ISA sample sizes as the trial progresses due to the ability to borrow placebo and treatment-effect information
- provide potential site benefit based on multiple therapies offered, and
- offer continuous screening of participants for future interventions.

The proposed design provides many unique operational and statistical challenges as well as opportunities to make the best decisions in advancing molecules through the drug development process.

The primary efficacy analysis is a Bayesian mixed-model repeated measures (MMRM) method that allows the borrowing of placebo information within a DSA and borrowing of treatment difference information between different addendum pain types. The amount of borrowing and the statistical methodology used to accommodate the borrowing (for example, pooling of data, hierarchical modeling), including the specifics of the Bayesian prior distributions, will be specified within each ISA.

The master protocol also allows for adaptations specified within an ISA. The adaptations may include stopping for early futility, stopping for early efficacy, sample size re-estimation, or removal of a dose arm.

Intervention-specific design elements are described in the respective ISA.

Efficacy Assessments

The master protocol contains a core set of assessments based on the Initiative on Methods, Measurement, and Pain Assessment in Clinical Trials (IMMPACT) guidelines (Dworkin et. al. 2005). The recommended domains when designing chronic pain clinical studies are

- pain
- physical functioning
- emotional functioning
- participant ratings of overall improvement
- adverse events (AEs), and
- participant disposition.

The NRS was selected for the primary endpoint based on its demonstrated ability to detect changes in pain and its common use across the disease states under study.

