5.4.1. Participation in Multiple ISAs

Interested participants will have the opportunity to participate in multiple ISAs within the same disease state or for different disease states.

Participation in multiple ISAs is allowed if the participant

- meets all inclusion or exclusion criteria for the master protocol, the applicable DSA, and the respective ISA at the time of screening
- has not participated in another ISA with the same intervention
- has completed the 30-day waiting period since participating in another clinical study involving an intervention
 - EXCEPTION – if the participant did not receive intervention, then the participant does not need to complete the 30-day waiting period

- has completed all previous ISAs without early discontinuation
 - EXCEPTION – if the participant discontinues without receiving intervention.

The intervention that the participant received in a previous ISA will have no impact on the randomization of treatment to the current ISA. The number of participants who will participate in multiple ISAs is unknown. Participation in more than one ISA, referred to as 'repeat participation,' will be tracked at the site level, the ISA level, and at the overall master protocol level.

Repeat participation may introduce the potential concern that populations between ISAs may be too homogenous or introduce potential biases into the participant population for future ISAs, such as inflation or deflation of placebo response in repeat participants, or bias of completers in the data set. If these issues occur, edits will be made to future amendments of the Master Protocol or an ISA to address this concern.

6. Study Intervention

Study intervention is defined as any investigational intervention(s), marketed product(s), placebo, or medical device(s) intended to be administered to a study participant according to the study protocol.

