9.4.2. Primary Endpoint and Analysis

The primary efficacy measure will be the same across all disease states and ISAs.

The primary efficacy analysis for an ISA will be conducted when all participants randomized to the ISA have completed the placebo-controlled portion of the ISA. The follow-up period may vary by ISA. Therefore, the primary efficacy analysis may be conducted prior to conclusion of the ISA and the collection of all follow-up data.

The primary efficacy analysis will be performed using a Bayesian MMRM method where the baseline information is modeled as a dependent variable. The baseline estimated means will be constrained to be the same between treatment groups due to randomization (Liang and Zeger, 2000). The primary efficacy analysis of the ISA of interest will be conducted on either the modified intention to treat (mITT) population or enhanced ITT population (see Section 9.3). The enhanced ITT population includes participant level data from ongoing ISAs and/or ISAs that have completed. Participants from ongoing ISAs must have had the opportunity to complete the placebo-controlled portion of the ISA to be included in the primary efficacy analysis for the ISA of interest. The ISA SAP will define the exact participant population included in the primary efficacy analysis.

The Bayesian CSF for the primary efficacy analysis will be defined in the ISA SAP for each respective ISA. The 95% credible intervals will be provided for the key parameters of interest.

This table describes information related to the primary efficacy measure.

Primary Efficacy Measure	Mean change from baseline to endpoint for average pain intensity as measured by the NRS. The exact endpoint for each ISA will be defined in the ISA SAP and may be defined, for example, as the last time point, the average of the last 2 time points, etc.
Data Collection	The NRS average pain will be collected daily. Average scores will be calculated over weekly and biweekly time intervals and will be available for analysis. The average of the weekly time-interval will be used for the primary efficacy analysis.
Primary Analysis	Efficacy of the active treatment(s) compared with placebo
Analysis Method	Bayesian MMRM analysis
Outcome Variable	The raw baseline and postbaseline values will be included in the response vector when fitting the statistical model. The change from baseline will be assessed via the statistical model.

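### Does a participant-by-ISA random effect fail to account for people who take part in more than one ISA?

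*Protocol*

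**What the plan says.** Section 9.4.1 provides that, when the primary dataset contains repeat participants, "all available data for the repeat participants will be included and used in the model". To account for them, "A participant by ISA-specific random effect (or other appropriate adjustments) will be added to the primary efficacy analysis model", with details in each ISA SAP. The same section also gives the ISA SAP the Bayesian model and exact priors whenever borrowing is used.

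One person's records from two ISAs can meet in one model because, in Section 9.4.2, "The enhanced ITT population includes participant level data from ongoing ISAs and/or ISAs that have completed". Section 9.4.2.1 limits placebo borrowing to ISAs within one disease state.

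Section 5.4.1 allows repeat participation and states that "The number of participants who will participate in multiple ISAs is unknown". It adds that "The intervention that the participant received in a previous ISA will have no impact on the randomization of treatment to the current ISA". It requires that the person "has not participated in another ISA with the same intervention", and says that repeat participation "will be tracked at the site level, the ISA level, and at the overall master protocol level".

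**The concern.** A random effect indexed by participant and ISA gives a repeat participant a separate draw in each ISA. If the draws are independent, the model treats that person as two unrelated people. Within an ISA the term then adds little, because a flexible repeated-measures covariance already carries the within-person correlation. On that reading the one term named for the job does not do it.

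Borrowing is where this would count. Section 4.2 expects the design to "facilitate smaller ISA sample sizes as the trial progresses due to the ability to borrow placebo and treatment-effect information", and later ISAs are also where repeats can accumulate. A wrong standard error for the comparison with borrowed placebo would shift the posterior probability used in the success criterion. Because each ISA has its own SAP, an unclear default in the master protocol could be copied several times.

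**Working it through.** **Inputs.** The protocol gives no sample size, allocation ratio, repeat rate or correlation that can be used here: Section 9.2 leaves sample size to each ISA, and Section 5.4.1 says the repeat number is unknown. There is therefore no stated figure to reproduce. Everything below is assumed except the two rules from Section 5.4.1, that earlier assignment does not affect randomization and that the same intervention may not be repeated.

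**Step 1: covariance by reading of the term.** Take between-person variance 2 and residual variance 1, so the total is 3.

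| Structure | Cross-ISA correlation |
|---|---|
| Participant-by-ISA, independent levels | 0/3 = 0 |
| Participant-by-ISA, levels correlated 0.3 | 0.3 × 2/3 = 0.20 |
| Participant-by-ISA, levels correlated 0.5 | 0.5 × 2/3 = 0.33 |
| Shared effect (1) plus participant-by-ISA effect (1) | 1/3 = 0.33 |
| Shared participant effect only | 2/3 = 0.67 |

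The zero comes from the independence assumption, which Section 9.4.1 does not state.

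**Step 2: number of overlapping people.** Assume 100 active and 50 placebo in the current ISA (150 in all), 100 donor placebo participants fully pooled, and 10% to 30% of the 150 as repeats (15 to 45 people). If donor ISAs were randomized 2:1 and both arms return equally, one third of the repeats were placebo donors. That is 5 to 15 people (3.3% to 10% of 150), split as 3 active + 2 placebo up to 10 + 5.

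**Step 3: standard error if the link is ignored.** Let nA = 100, let N = 50 + 100 = 150 be the pooled placebo number, and let mA and mP be the current active and current placebo participants who are also donors. Let r be the cross-ISA correlation of baseline-adjusted outcomes. In units of the adjusted variance:

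- Reported: V0 = 1/nA + 1/N = 1/100 + 1/150 = 0.016667.
- True: V = V0 − 2·r·mA/(nA·N) + 2·r·mP/N².

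If repeats are the same fraction f of each arm, the two added terms sum to −2·r·f·nB/N², where nB is the number of donors. This is negative for any positive r, so the reported standard error is too large.

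When only a person's level carries over (shared intercept), r = ρ(1 − w)/(1 + w), where ρ is the raw cross-ISA correlation and w the baseline-to-endpoint correlation.

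- ρ = 0.4, w = 0.7: r = 0.4 × 0.3/1.7 = 0.0706. With 3 + 2 repeats, V = 0.016667 − 0.0000282 + 0.0000125 = 0.016651. True/reported SE = √(0.016651/0.016667) = 0.9995.
- ρ = 0.6, w = 0.6: r = 0.6 × 0.4/1.6 = 0.15. With 10 + 5 repeats, V = 0.016667 − 0.0002 + 0.0000667 = 0.016533. Ratio = 0.9960.

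The reported SE is thus 0.05% to 0.4% too large (1/0.9995 and 1/0.9960). A nominal one-sided 5% becomes 4.99% to 4.93%.

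If change from baseline carries over too, r is the full correlation. With r = 0.6 and 10 + 5 repeats, V = 0.016667 − 0.0008 + 0.000267 = 0.016133. The ratio is 0.9839, so the reported SE is 1.6% too large.

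Exact generalised least squares on the 250 records gives the same ratios. A full model with baseline and 8 weekly means, under the shared intercept, gives 0.9966 to 0.9995.

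**Step 4: what the linked model would gain.** From the same least-squares calculation, the correct model's SE divided by the reported SE is:

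| Case | 3 + 2 repeats | 10 + 5 repeats |
|---|---|---|
| Shared intercept, ρ 0.4, w 0.7 | 0.9986 | 0.9952 |
| Shared intercept, ρ 0.6, w 0.6 | 0.9931 | 0.9771 |
| Change also correlated, 0.4 | 0.9934 | 0.9773 |
| Change also correlated, 0.6 | 0.9838 | 0.9476 |

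With hierarchical borrowing instead of pooling (between-ISA SD 0.1 to 0.2 of the NRS SD, shared intercept), the error is at most 0.14% and the gain 0.1% to 1.4%.

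These gains treat the cross-ISA covariance as known. With n pairs, a correlation of 0.4 has an approximate standard error of (1 − 0.16)/√(n − 1): 0.84/√4 = 0.42 for 5 pairs and 0.84/√14 = 0.22 for 15. The parameter would rest largely on its prior, so the gains are upper bounds.

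**The case for a change.** The strongest case for a change is that the master protocol picked this example itself, each ISA SAP may copy it, and one sentence would settle it with no new data, since repeats are already tracked. The best cell above, 0.9476, is worth about 10% in information (1 − 0.9476² = 0.102). Nor is the conservative direction guaranteed in one realised sample. If the overlap fell only in the own placebo arm (5 to 10 people), true/reported SE would be 1.001 to 1.016. In a harsher case, with 20 such people, 50 borrowed placebo participants and correlation 0.6, it would be 1.058, and a one-sided 5% would become about 6.0%.

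The algebra stands, and so does the remark that the wording could be clearer. The rest carries less weight. Placebo-only overlap is not the expected pattern, because earlier assignment does not affect randomization. The 10% figure needs 30% repeats, full pooling, a correlation of 0.6 in change between separate studies and a known covariance. Any such gain is open under the present text, because correlated ISA-specific effects fit its words and other adjustments are allowed.

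A firmer sentence could also do harm. Prescribing a shared participant effect would not suit the prior-based borrowing in Section 9.4.2.1 where donor data enter as a prior and not as rows in the model. A shared intercept also leaves raw changes from baseline uncorrelated across ISAs, although change is the endpoint. Under Section 9.4.1 only a change to a principal feature needs an amendment, and Section 10.1.1 requires ethics approval for amendments, so the ISA SAP is the natural place for this choice.

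**Conclusion.** No change is needed. Section 9.4.1 recognises the problem, states what the adjustment is for, names one form, allows others and leaves the specification to the ISA SAP. Whether the person-level effects are correlated across ISAs is a detail that an analyst writing that SAP would settle sensibly.

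If an ISA SAP did use independent levels in a joint model with pooled placebo, the reported SE would be 0.05% to 0.4% too large in the main case and about 1.6% too large if change also carries over strongly, on the conservative side when both arms contain repeats in proportion. These sizes rest on assumed sample sizes, repeat rates and correlations.

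The reach is narrow. The ISA-only analyses in Section 9.4.3.1 are unaffected. Treatment-effect borrowing for one intervention shares no repeat participants, because the same intervention may not be taken twice. Section 9.4.8 already requires sensitivity analyses on borrowing.

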9.4.1.1. Missing Data

The NRS value of average pain and worst pain over the past 24 hours will be collected daily for each participant. For the statistical analyses, the average NRS value of the average and worst pain over the past 24 hours will be calculated for both weekly intervals and biweekly intervals.

The average of the weekly intervals for the NRS will result in 8 postbaseline observations, and the average of the biweekly intervals will result in 4 postbaseline observations for each participant if a participant completes the placebo-controlled portion of the study.

The average of the weekly intervals for the NRS will be used in the primary efficacy analysis and other analyses described below, unless otherwise specified in the SAP.

A participant must have 50% or greater of the daily NRS values during the prespecified time interval to calculate the average NRS value; otherwise, the average NRS value for that visit will be considered missing.

Missing data for other variables and analyses will be described in the master protocol SAP.

For all Bayesian analyses, the missing values will be accounted for naturally using the Bayesian imputation of missing values.

9.4.2. Primary Endpoint and Analysis

The primary efficacy measure will be the same across all disease states and ISAs.

The primary efficacy analysis for an ISA will be conducted when all participants randomized to the ISA have completed the placebo-controlled portion of the ISA. The follow-up period may vary by ISA. Therefore, the primary efficacy analysis may be conducted prior to conclusion of the ISA and the collection of all follow-up data.

The primary efficacy analysis will be performed using a Bayesian MMRM method where the baseline information is modeled as a dependent variable. The baseline estimated means will be constrained to be the same between treatment groups due to randomization (Liang and Zeger, 2000). The primary efficacy analysis of the ISA of interest will be conducted on either the modified intention to treat (mITT) population or enhanced ITT population (see Section 9.3). The enhanced ITT population includes participant level data from ongoing ISAs and/or ISAs that have completed. Participants from ongoing ISAs must have had the opportunity to complete the placebo-controlled portion of the ISA to be included in the primary efficacy analysis for the ISA of interest. The ISA SAP will define the exact participant population included in the primary efficacy analysis.

The Bayesian CSF for the primary efficacy analysis will be defined in the ISA SAP for each respective ISA. The 95% credible intervals will be provided for the key parameters of interest.

This table describes information related to the primary efficacy measure.

Primary Efficacy Measure	Mean change from baseline to endpoint for average pain intensity as measured by the NRS. The exact endpoint for each ISA will be defined in the ISA SAP and may be defined, for example, as the last time point, the average of the last 2 time points, etc.
Data Collection	The NRS average pain will be collected daily. Average scores will be calculated over weekly and biweekly time intervals and will be available for analysis. The average of the weekly time-interval will be used for the primary efficacy analysis.
Primary Analysis	Efficacy of the active treatment(s) compared with placebo
Analysis Method	Bayesian MMRM analysis
Outcome Variable	The raw baseline and postbaseline values will be included in the response vector when fitting the statistical model. The change from baseline will be assessed via the statistical model.
Fixed Categorical Effects in Model	
 • Time interval • Interaction of treatment by time interval without the baseline • Average baseline pain severity category (moderate or mild vs severe), defined by baseline NRS <7 vs baseline NRS ≥7 • Pooled investigative site
Additional Covariates in Model	Any stratification variable used for randomization of the ISA of interest will also be included in the model. Additional covariates may also be specified at an ISA level.

Abbreviations: ISA = intervention-specific appendix; MMRM = mixed-model repeated measures; NRS = numeric rating scale; SAP = statistical analysis plan.

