9.1. Statistical Hypotheses

For each ISA in this master protocol, a Bayesian critical success factor (CSF) will be defined in the ISA and used to evaluate whether the ISA met its primary endpoint. The CSF will be evaluated for the primary efficacy endpoint, average pain intensity as measured by the NRS, using the methodology described in Section 9.4.2 and will be calculated at the conclusion of the double-blind portion of each ISA within the master protocol.

The CSF will have the general form of:

- probability (treatment effect < effect of interest) > probability threshold.

The treatment effect will be defined as the LY estimate–placebo estimate of the change from baseline at endpoint. The effect of interest is typically found through a literature search or clinical judgement. The probability threshold is generally set to have a desired level of confidence in the treatment effect or to have the desired operating characteristics under a range of plausible, assumed drug effect scenarios of truth, including a null effect.

Additional hypotheses will include the comparison of each active intervention with placebo for the prespecified objectives and endpoints defined in Section 3.

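### Does it matter that the Protocol places the critical success factor in the ISA in one section and in the ISA SAP in another?

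*Protocol*

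**What the plan says.** On the CSF, Protocol Section 9.1 states that "a Bayesian critical success factor (CSF) will be defined in the ISA and used to evaluate whether the ISA met its primary endpoint". Section 9.4.2 states: "The Bayesian CSF for the primary efficacy analysis will be defined in the ISA SAP for each respective ISA". Section 9.1 also fixes the general form of the criterion: the posterior probability that the treatment effect lies below an effect of interest must exceed a threshold.

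On priors and borrowing, Section 4.2 says that the amount and method of borrowing, "including the specifics of the Bayesian prior distributions, will be specified within each ISA". Section 9.4.1 lists among the contents of the ISA SAP, where borrowing is used, "the Bayesian model and exact prior distributions used for the primary efficacy analysis and other Bayesian secondary analyses".

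On precedence, Section 9.4.1 has one rule: "If there is a discrepancy between the master protocol SAP and the ISA SAP, the methodology in the ISA SAP will be used". On timing it says: "The ISA SAP will be finalized prior to the first unblinding of the respective ISA".

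Section 9.2 asks for the sample size, power and false positive rate to be given and justified in the ISA. It defines the false positive rate as how often the CSF is met when the true effect is zero at all postbaseline visits.

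**The concern.** Sections 9.1 and 9.4.2 each name one home for the decision rule, and not the same one. The Protocol does treat the ISA and the ISA SAP as separate documents: Sections 9.3 and 9.5 offer them as alternatives. One might answer that ISA in Section 9.1 means the sub-study, but the term is also used for the document, as in Section 4.2: "Intervention-specific design elements are described in the respective ISA".

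The worry is about what happens if the two documents differ. The false positive rate is justified in the ISA and belongs to one particular CSF, prior and borrowing scheme. If the CSF that counts sits in a document that need be final only by first unblinding, it could move away from what was simulated. No sentence says which version then decides success, and none requires the operating characteristics to be restated. Section 9.4.2.1 foresees that borrowing decisions may vary over the life of the platform, which Section 4.1 puts at an estimated 5 to 7 years for entry of interventions.

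**Working it through.** **The CSF.** Section 9.1 says ISA; Section 9.4.2 says ISA SAP. Neither says only, and neither excludes the other. The statements conflict only if the two documents carry different criteria. Much is already fixed at master level: the general form (9.1), the endpoint measure (average pain on the NRS) and the model class (9.4.2). For the criterion itself, the effect of interest and the probability threshold remain to be set, and writing the same two values in both documents satisfies both sections.

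**Priors and borrowing.** Section 4.2 says within each ISA; Section 9.4.1 says ISA SAP. Section 9.4.2.1 joins them: each ISA has the flexibility to define how much it borrows, and does so by specifying the priors in its ISA SAP. The same section puts the exact specification of model and parameters in the ISA SAP. Read with this, Section 4.2 is a summary in a rationale section. What remains of the clash is the CSF wording alone.

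**Precedence.** The rule in Section 9.4.1 covers the master protocol SAP against the ISA SAP. No rule covers the ISA against its own SAP. That gap is real.

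**Does the stated false positive rate depend on which CSF is used?** Yes, in any design. Assume a flat prior, a normally distributed estimate with standard error SE, and no borrowing. Write d0 for the effect of interest, p for the threshold and z_p for the normal quantile. The CSF is met when the estimate falls below d0 − z_p·SE, so at a true effect of 0

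false positive rate = Φ(d0/SE − z_p).

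| d0 | p | SE | d0/SE − z_p | Rate |
|---|---|---|---|---|
| 0 | 0.90 | any | −1.282 | 10% |
| 0 | 0.95 | any | −1.645 | 5% |
| 0 | 0.975 | any | −1.960 | 2.5% |
| −0.5 | 0.95 | 0.3 | −1.667 − 1.645 = −3.312 | 0.05% |
| −0.5 | 0.95 | 0.4 | −1.250 − 1.645 = −2.895 | 0.19% |
| −0.5 | 0.95 | 0.5 | −1.000 − 1.645 = −2.645 | 0.41% |

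Every input is assumed; the Protocol states no threshold, effect of interest, SD or sample size. The table shows that a rate quoted for one criterion does not carry over to another. It says nothing about whether any ISA has two criteria.

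**What a sponsor following the text would do.** Section 9.2 obliges it to simulate the operating characteristics for the ISA. That cannot be done without a CSF, so a CSF exists at the design stage. The ISA SAP then states it and is finalized before that ISA is first unblinded. On departures from the master protocol's analysis methods that fall short of a principal feature, Section 9.4.1 adds: "Any other change to the data analysis methods, and the justification for making the change, will be described in the respective SAP". It asks for the same account in that ISA's study report. The criterion is therefore settled before anyone could choose it on the results.

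**The case for a change.** The strongest case for a change is that this is no complaint about leaving detail to a SAP. The Protocol names two homes for the rule that decides success, the flaw is visible in this document alone, and no unseen ISA SAP can alter the text. A short edit would remove the doubt for every present and future ISA.

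The textual point stands: Sections 9.1 and 9.4.2 differ, and no rule ranks the ISA against its SAP. The consequence does not. Harm needs an ISA and an ISA SAP that disagree, and neither is at hand.

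The obvious edit also brings no clear gain. Making the ISA SAP the sole home, which is the smaller wording change, moves the CSF wholly into the document with the later deadline and away from the ISA, where Section 9.2 wants the false positive rate defined through it. That works against the worry that prompted it. A clause requiring re-simulation after any departure would offset this, but it is a new obligation written for a hypothetical case. Section 9.2 already calls for simulation over a range of effects and prior specifications.

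On borrowing in particular, Section 9.4.3.1 requires analyses of NRS average pain from the ISA's own data without borrowing, and Section 9.4.8 requires sensitivity analyses of the impact of borrowing. A reader could see how far the result leans on the borrowing choice whichever document sets it.

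**Conclusion.** The two sections are worded inconsistently and one precedence rule is absent. This is a clerical matter that a competent team resolves by stating the same CSF in both documents. No conflicting criterion is shown, and no result or error rate of this trial is shown to change. The priors and borrowing wording is largely reconciled by Section 9.4.2.1 and adds little.

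The conclusion assumes that each ISA is simulated as Section 9.2 requires and that its SAP is finalized before first unblinding as Section 9.4.1 requires. If a particular ISA and its SAP were found to state different criteria, that would be a finding about those documents. On the master protocol alone, no change follows.
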